# **Hepatic toxicity**

Table C4. Cohort C hepatic toxicity management guidelines

Event	Actions
Grade 3 ALT/AST or Grade 3	• Withhold olaparib for up to 28 days until recovery to Grade ≤1 (or
bilirubin	Grade ≤2 in patients with Grade 2 ALT at baseline).
	Look for alternative causes.
	Reduce olaparib to the next dose reduction level.
	• If symptoms do not recover to Grade ≤1 (or Grade ≤2 in patients
	with Grade 2 ALT at baseline) within 28 days, discontinue olaparib.
Grade 4 ALT/AST or Grade 4	Permanently discontinue olaparib.
bilirubin	Evaluate alternative cause.

AST or ALT >3 x ULN	Withhold olaparib. Please refer to Section 16.8 for further
AND	information on evaluation and reporting requirements for potential

 
Total bilirubin >2 x ULN
 
	Hy's Law cases.
	• Evaluate the patient as soon as possible (within 48 hours if
	possible). All cases confirmed on repeat testing with no alternative
	explanation for abnormal liver function should be considered
	potential Hy's Law cases.
	Report as an SAE.
	Discontinue trial treatment if Hy's Law confirmed.
	If the criteria for Hy's Law are not met, follow the guidance above
	for Grade 3/4 ALT/AST or bilirubin.

# 25.2.4. Part 2 Olaparib: Dose interruptions

In addition to the specific toxicity management guidelines within Section 25.2.3 olaparib treatment should be interrupted if patients experience any Grade ≥3 toxicity.

Following an interruption for Grade  $\geq 3$  toxicity, olaparib should be delayed for up to 28 days until these toxicities have resolved to Grade  $\leq 1$  or returned to baseline.

Repeat dose interruptions are allowed as required, for a maximum of 28 days on each occasion. If a patient remains off olaparib for >28 days, olaparib should be permanently discontinued.

# 25.2.5. Part 2 Olaparib: Prescription and Dispensing

Olaparib tablets will be provided in non-patient-specific bottles. The patient's Trial ID should be recorded on the bottle label prior to dispensing. Patients should be instructed to keep their trial treatment in the bottles provided and not transfer it to any other container.

All efforts should be made to ensure that patients clearly understand the directions for self-medication. Patients should be given a sufficient supply and unused trial treatment and/or empty bottles should be returned at the appropriate time points. Returned unused trial treatment must not be redispensed to any patient and should only be destroyed with prior approval from ICR-CTSU according to local destruction policy.

Olaparib should be prescribed by the PI or Co-investigator and dispensed by the hospital pharmacy from trial stock supplied specifically for use within PHOENIX only.

# 25.2.6. Part 2 Olaparib: Patient Cards and Treatment Diary Cards

A small wallet sized patient card template will be provided by ICR-CTSU for completion by the participating site. Each card will state:

- The name of the participating site
- That the patient is participating in the PHOENIX trial
- That the patient is taking olaparib (and durvalumab if applicable)
- An emergency site contact number

IRAS Project Number: 249774

Patients should be advised to keep their patient card in their possession at all times.

A treatment diary card will be provided by ICR-CTSU for completion by the patient, in order to record the number of olaparib tablets taken on each day of trial treatment.

# 25.2.7. Part 2 Olaparib: Permitted Concomitant Therapy

All medication considered necessary for the participants' welfare and which is not expected to interfere with the evaluation of the trial treatment may be given at the discretion of the investigator. All concomitant medications must be recorded in the patient's notes, as well as the appropriate eCRF pages within the clinical database.

The use of any natural/herbal products or other traditional remedies should be discouraged, but use of these products, as well as use of all vitamins, nutritional supplements, and all other concomitant medications must be recorded in the eCRF.

Bisphosphonates, RANK ligand antagonists (e.g. denosumab) and blood transfusions should be given as required at the discretion of the Investigator.

Patients may take corticosteroids but increased vigilance is recommended on electrolyte and glucose levels.

Patients who require anti-coagulation during trial treatment should start on LMWH.

#### 25.2.8. Part 2 Olaparib: Non-permissible Medications/Therapies

No other anti-cancer therapy (chemotherapy, immunotherapy, radiotherapy, biological therapy or other novel agent) is to be permitted while the patient is receiving trial treatment with olaparib ± durvalumab. Concurrent use of hormones for non-cancer-related conditions (e.g., insulin for diabetes and hormone replacement therapy) is acceptable. **Please note:** patients may receive adjuvant radiotherapy as per SOC post-operatively during PART 1 but this must be completed at least three weeks prior to commencement of any trial treatment in PART 2.

Live virus and live bacterial vaccines should not be administered whilst the patient is receiving trial treatment and during a period of 30 days following the last dose of trial treatment. An increased risk of infection by the administration of live virus and bacterial vaccines has been observed with conventional chemotherapy drugs and the effects with olaparib are unknown.

#### PLEASE REFER TO APPENDIX 5 FOR PROHIBITED CONCURRENT MEDICATIONS FOR OLAPARIB.

It is recommended that known potent inhibitors/inducers of CYP3A are not co-administered with olaparib. Please see Appendix 5 for details. The required washout period prior to commencing trial treatment is 5 weeks for known strong or moderate CYP3A inhibitors or inducers. Please refer to Section 8.1.2 Trial Entry Exclusion Criteria for further information.

Caution should be exercised when substrates of CYP3A4 or UGT1A1 are combined with olaparib, in particular those with a narrow therapeutic margin. Caution should be exercise if olaparib is administered in

IRAS Project Number: 249774

combination with P-gp inhibitors which may increase exposure to olaparib. Caution should be exercised if olaparib is administered in combination with any statin. **Please see Appendix 5 for additional guidance.** 

Based on limited *in vitro* data, olaparib may increase the exposure to substrates of CYP3A4, P-gp, OATP1B1, OCT1, OCT2, OAT3, MATE1 and MATE2K. Based on limited *in vitro* data, olaparib may reduce the exposure to substrates of CYP3A4, CYP1A2, 2B6, 2C9, 2C19 and P-gp. **Please see Appendix 5 for examples of substrates.** 

The efficacy of hormonal contraceptives may be reduced if co-administered with olaparib.

#### **Anticoagulant Therapy**

Patients who are taking warfarin may participate in this trial; however, it is recommended that international normalised ratio (INR) be monitored carefully at least once per week for the first month, then monthly if the INR is stable. Subcutaneous heparin and low molecular weight heparin are permitted.

#### Anti-emetics/Anti-diarrhoeals

If a patient develops nausea, vomiting and / or diarrhoea, then these symptoms should be reported as AEs (see Section 16) and appropriate treatment of the event given.

### Administration of other anti-cancer agents

With the exception of pembrolizumab, if being received as part of SOC, patients must not receive any other concurrent anti-cancer therapy, including investigational agents, while on trial treatment during Part 1.

#### 25.2.9. Part 2 Olaparib: Additional Cautions

Because the AEs related to olaparib may include asthenia, fatigue and dizziness, patients should be advised to use caution while driving or using machinery if these symptoms occur.

Olaparib is regarded as a compound with medium/high foetal risk. Please refer to Section 5.4 Lifestyle Guidance for guidance on the contraception requirements for participants within the PHOENIX trial.

# 25.2.10. Part 2 Olaparib: Missed Doses

The scheduled olaparib dose can be taken up to 2 hours after the scheduled dose time. If greater than 2 hours has passed, the missed dose should not be taken. If a dose is missed, olaparib should be resumed at the next scheduled dose. Missed doses should not be made up. If the patient vomits after taking a dose of olaparib they should be advised to resume treatment at the next scheduled dose.

#### 25.2.11. Part 2 Olaparib: Overdoses

There is currently no specific treatment in the event of an overdose with olaparib and possible symptoms of overdose are not established. If overdose occurs, this should be managed symptomatically. Please contact the ICR-CTSU Trial Team for advice.

Olaparib must only be used in accordance with the dosing recommendations in this protocol. Any dose or frequency of dosing that exceeds the dosing regimen specified in this protocol should be reported as an overdose. The Maximum Tolerated Dose is 300 mg twice daily (tablet).

IRAS Project Number: 249774

Adverse reactions associated with overdose should be treated symptomatically and should be managed appropriately.

#### 25.2.12. Part 2 Olaparib: Compliance

Patients must be asked to bring all their trial treatment and diary card when they attend the clinic for the purposes of treatment compliance assessment and drug accountability. Every effort should be made to encourage patients to return the unused trial treatment and empty bottles. The unused tablets should be collected by the Investigator/Research Nurse and counted to ascertain patient compliance, trial treatment will then be returned to pharmacy for drug accountability. Drug destruction should only be carried out with prior approval from ICR-CTSU and according to local destruction policy.

### 25.2.13. Part 2 Olaparib: Supply and Distribution of Olaparib

Olaparib is manufactured and provided free of charge by AZ to participating sites.

No trial treatment will be distributed to participating sites unless ICR-CTSU is satisfied that the required approvals and agreements and initiation procedures are complete.

# 25.2.14. Part 2 Olaparib: Formulation, Packaging, Storage Conditions and Labelling

Olaparib will be supplied as oval film-coated tablets supplied in HDPE bottles containing desiccant. Bottles are secured with a child-resistant closure; induction-sealed membranes provide tamper evidence. Olaparib tablets should be stored below 30°C. Tablets should be stored in the bottles provided and taken according to the instructions on the label.

The drug distribution company is responsible for labelling olaparib in accordance with the MHRA approved trial label. Pharmacies may add their own hospital dispensing label to the trial treatment but should not obscure the existing label on the trial treatment packaging.

#### 25.3. Part 2 Durvalumab: Trial Treatment

#### 25.3.1. Part 2 Durvalumab: Dose and Schedule

Based on average body WT of 75 kg, a fixed dose of 1,500mg Q4W durvalumab (equivalent to 20 mg/kg Q4W) should be administered via IV infusion on Day 1 of each 28 day treatment cycle.

#### First infusion of durvalumab:

On the first infusion day, patients should be monitored and vital signs collected/recorded prior to, during and after infusion of durvalumab. BP and pulse will be collected from patients before, during, and after each infusion at the following times (based on a 60-minute infusion):

- Prior to the beginning of the infusion (measured once from approximately 30 minutes before up to 0 minutes [i.e., the beginning of the infusion])
- Approximately 30 minutes during the infusion (halfway through infusion)
- At the end of the infusion (approximately 60 minutes ±5 minutes)

IRAS Project Number: 249774

If the infusion takes longer than 60 minutes, then BP and pulse measurements should follow the principles as described above or be taken more frequently if clinically indicated. A 1-hour observation period is recommended after the first infusion of durvalumab.

Trial treatment should be administered as per the above schedule, however if this is not possible due to unavoidable circumstances (i.e. bank holidays) from Cycle 2 onwards Day 1 of trial treatment may be delayed for up to 3 days after the due date for Cycle 2, or delayed for up to 7 days after the due date for Cycle 3 onwards.

For further guidance on trial treatment delay due to toxicity please refer to Sections 25.3.2, 25.3.3 and 25.3.4.

#### Subsequent infusions of durvalumab

Blood pressure, pulse and other vital signs should be measured, collected/recorded prior to the start of the infusion. Patients should be carefully monitored and BP and other vital signs should be measured during and post infusion as per institution standard and as clinically indicated.

#### 25.3.2. Part 2 Durvalumab: Dose Modifications

Every effort should be made to administer durvalumab as per the planned schedule. Any toxicity observed during the course of the trial treatment should be managed by interruption of durvalumab, as deemed appropriate by the Investigator. Patients experiencing toxicities related to durvalumab may have their dose modified as outlined in this section. Further guidance on specific toxicities requiring dose modifications are described in Section 25.3.3 and Appendix 7.

# 25.3.3. Part 2 Durvalumab: Specific Toxicities Requiring Dose Modifications

Guidelines for the management of immune-mediated reactions, infusion-related reactions, and non-immune-mediated reactions for durvalumab monotherapy are provided in the **Dosing Modification and Toxicity Management Guidelines at Appendix 7**. Patients should be thoroughly evaluated and appropriate efforts should be made to rule out neoplastic, infectious, metabolic, toxin, or other etiologic causes of the imAE. Serologic, immunologic, and histologic (biopsy) data, as appropriate, should be used to support an imAE diagnosis. In the absence of a clear alternative etiology, events should be considered potentially immune related.

The following general guidance should be followed for management of toxicities:

- Treat each of the toxicities with maximum supportive care (including holding the agent suspected of causing the toxicity if required).
- If the symptoms promptly resolve with supportive care, consideration should be given to
  continuing the same dose of durvalumab along with appropriate continuing supportive care. If
  medically appropriate, dose modifications are permitted.
- All dose modifications should be documented with clear reasoning and documentation of the approach taken.

All toxicities will be graded according to NCI CTCAE, v5.0.

IRAS Project Number: 249774

Following the first dose of durvalumab, subsequent administration of durvalumab can be modified based on toxicities observed, as described in the **Dosing Modification and Toxicity Management Guidelines** at Appendix 9.

Dose reductions are not permitted. In case of doubt, the Investigator should consult with the ICR-CTSU Trial Team.

# **Eyes**

For signs and symptoms suggestive of keratitis or uveitis (such as acute or worsening eye inflammation, lacrimation, light sensitivity, blurred vision, eye pain and /or red eye), subjects should be advised to seek medical advice promptly, and, if required, referred promptly to an ophthalmologist. AEs related to the eye may be immune related and should be managed according to local practice. Please also refer to the Dosing Modification and Toxicity Management Guidelines at Appendix 9.

# 25.3.4. Part 2 Durvalumab: Dose interruptions

As directed in Section 25.3.3 and the **Dosing Modification and Toxicity Management Guidelines** at Appendix 7, durvalumab treatment should be interrupted if patients experience any Grade ≥2 toxicity.

Following an interruption for Grade ≥2 toxicity, trial treatment may be delayed for up to 12 weeks until these toxicities have resolved to Grade ≤1 or returned to baseline.

Repeat dose interruptions are allowed as required, for a maximum of 12 weeks on each occasion. If a patient remains off trial treatment for >12 weeks, trial treatment should be permanently discontinued.

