# Dosing Modification and Toxicity Management Guidelines (TMGs) for Durvalumab Monotherapy, Durvalumab in Combination with other Products, or Tremelimumab Monotherapy –August 2024

#### General Considerations Regarding Immune-Mediated Reactions

These guidelines are provided as a recommendation to support investigators in the management of potential immune-mediated adverse events (imAEs).

Immune-mediated events can occur in nearly any organ or tissue, therefore, these guidelines may not include all the possible immune-mediated reactions. Investigators are advised to take into consideration the appropriate practice guidelines and other society guidelines (e.g., National Comprehensive Cancer Network (NCCN), European Society of Medical Oncology (ESMO)) in the management of these events. Refer to the section of the table titled "Other-Immune-Mediated Reactions" for general guidance on imAEs not noted in the "Specific Immune-Mediated Reactions" section.

Early identification and management of imAEs is essential to ensure safe use of the study drug. Monitor patients closely for symptoms and signs that may be clinical manifestations of underlying imAEs. Patients with suspected imAEs should be thoroughly evaluated to rule out any alternative etiologies (e.g., disease progression, concomitant medications, infections). In the absence of a clear alternative etiology, all such events should be managed as if they were immune-mediated. Institute medical management promptly, including specialty consultation as appropriate. In general, withhold study drug/study regimen for severe (Grade 3) imAEs. Permanently discontinue study drug/study regimen for life-threatening (Grade 4) imAEs, recurrent severe (Grade 3) imAEs that require systemic immunosuppressivetreatment, or an inability to reduce corticosteroid dose to 10 mg or less of prednisone or equivalent per day within 12 weeks of initiating corticosteroids.

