	Grade 3 or 4	Permanently discontinue study drug/study	For Grade 3 or 4
		regimen.	
 
Hospitalize the patient
 

			
 
Promptly initiate empiric IV methylprednisolone 2 to 4 mg/kg/day or equivalent.
 

			
 
Obtain Pulmonary and Infectious Diseases Consults; consider discussing with Clinical Study Lead, as needed.
 

			
 
Consider starting anti-infective therapy if infection is still a consideration on the basis of other diagnostic testing despite negative culture results
 

			
 
Supportive care (e.g., oxygen).
 

			
 
If no improvement within 2 days, additional workup should be considered and prompt treatment with additional immunosuppressive therapy such as TNF inhibitors (e.g., infliximab at 5 mg/kg IV, may be repeated at 2 and 6 weeks after initial dose at the discretion of the treatingprovider or relevant practice guidelines). Caution: rule out sepsis and refer to infliximab label for general guidance before using infliximab.
 

Diarrhea/Colitis	Any Grade	General Guidance	For Any Grade
	(Refer to NCI CTCAE		
 
Patients should be thoroughly evaluated to rule out
 

	applicable version in		any alternative etiology (e.g., disease progression,

study protocol for defining the CTCAE grade/severity)		other medications, or infections), including testing for Clostridium difficile toxin, etc.  Monitor for symptoms that may be related to diarrhea/enterocolitis (abdominal pain, cramping, or changes in bowel habits such as increased frequency over baseline or blood in stool) or related to bowel perforation (such as sepsis, peritoneal signs, and ileus).  Consider further evaluation with imaging study with contrast.  Consult a gastrointestinal (GI) specialist for consideration of further workup.  WHEN SYMPTOMS OR EVALUATION INDICATE AN INTESTINAL PERFORATION IS SUSPECTED, CONSULT A SURGEON EXPERIENCED IN ABDOMINAL SURGERY IMMEDIATELY WITHOUT ANY DELAY.  PERMANENTLY DISCONTINUE STUDY DRUG FOR ANY GRADE OF INTESTINAL PERFORATION.  Steroids should be considered in the absence of clear alternative etiology, even for low-grade events, in order to prevent potential progression to higher grade events, including intestinal perforation.  Use analgesics carefully; they can mask symptoms of perforation and peritonitis.

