			assessment of early morning adrenocorticotropin hormone (ACTH), cortisol, TSH and free T4; also consider gonadotropins, sex hormones, and prolactin levels, as well as cosyntropinstimulation test (though it may not be useful in diagnosing early secondary adrenal insufficiency).  - If TSH < 0.5 × LLN, or TSH >2 × ULN, or consistently out of range in 2 subsequent measurements, include free T4 at subsequent cycles as clinically indicated and consider consultation of an endocrinologist.
	Grade 2, 3, or 4	- For Grade 2-4 endocrinopathies other	For Grade 2, 3, or 4
		than hypothyroidism and type 1 diabetes mellitus (T1DM), consider holding study drug/study regimen	
 
Consult endocrinologist to guide evaluation of endocrine function and, as indicated by suspected endocrinopathy and as clinically indicated, consider pituitary scan.
 

		dose until acute symptoms resolve.  - Study drug/study regimen can be resumed once patient stabilizes and after completion of steroid taper (<10 mg prednisone, or equivalent).  - Patients with endocrinopathies who	
 
For all patients with abnormal endocrine work up, except those with isolated hypothyroidism or T1DM, and as guided by an endocrinologist, consider short-term corticosteroids (e.g., 1 to 2 mg/kg/day methylprednisolone or IV equivalent) and prompt initiation of treatment with relevant hormone replacement.
 

		may require prolonged or continued steroid replacement (e.g., adrenal	
 
Isolated hypothyroidism may be treated with replacement therapy, without study drug/study regimen interruption, and without corticosteroids.
 

		insufficiency) can be retreated with study drug/study regimen if the patient is clinically stable as per investigator or treating physician's	
 
Isolated T1DM may be treated with appropriate diabetic therapy, and without corticosteroids. Only hold study drug/study regimen in setting of hyperglycemia when diagnostic workup is positive for diabetic ketoacidosis.
 

		clinical judgement.	
 
For patients with normal endocrine workup (laboratory assessment or magnetic resonance imaging (MRI) scans), repeat laboratory assessments/MRI as clinically indicated.
 

Amylase/Lipase increased	Any Grade	General Guidance	For Any Grade
	(Refer to NCI CTCAE		
 
Patients should be thoroughly evaluated to rule out any alternative etiology (e.g. disease progression,
 

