	Grade 2, 3 or 4	
 
If Grade 2-4, permanently discontinue study drug/study regimen.
 
	For Grade 2-4  Monitor symptoms daily, hospitalize.  Consider cardiology consultation and a prompt start of high-dose/pulse corticosteroid therapy  Supportive care (e.g., oxygen).  If no improvement consider additional immunosuppressive therapy such as TNF inhibitors (e.g., infliximab), IVIG or plasmapheresis or other therapies depending on the clinical condition of the patient, based on the discretion of the treating specialist consultant ror relevant practice guidelines.  Caution: It is important to rule out sepsis and refer to infliximab label for general guidance before using infliximab. Infliximab is contraindicated for patients who have heart failure.
Myositis/ Polymyositis	Any Grade (Refer to NCI CTCAE applicable version in study protocol for	General Guidance	For Any Grade  - Patients should be thoroughly evaluated to rule out any alternative etiology (e.g., disease progression, other medications, or infections).

	Manitan national for since and the first
defining the CTCAE grade/severity)	
 
Monitor patients for signs and symptoms of poly/myositis. Typically, muscle weakness/pain occurs in proximal muscles including upper arms, thighs, shoulders, hips, neck and back, and; also difficulty breathing and/or trouble swallowing can occur and progress rapidly. Increased general feelings of tiredness and fatigue may occur, and there can be new-onset falling, difficulty getting up from a fall, and trouble climbing stairs, standing up from a seated position, and/or reaching up.
 

	
 
If poly/myositis is suspected, a Neurology consultation should be obtained early, with prompt guidance on diagnostic procedures. Myocarditis may co-occur with poly/myositis; refer to guidance under Myocarditis. Given breathing complications, refer to guidance under Pneumonitis/ILD. Given possibility of an existent (but previously unknown) autoimmune disorder, consider Rheumatology consultation.
 

	
 
Consider, as necessary, discussing with the Clinical Study Lead.
 

	
 
Consider that patients may present with or progress to rhabdomyolysis. Treat signs and symptoms as per institutional protocol or local clinical practice.
 

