	
 
Initial work-up should include clinical evaluation, creatine kinase, aldolase, lactate dehydrogenase (LDH), blood urea nitrogen (BUN)/creatinine, erythrocyte sedimentation rate or C-reactive protein (CRP) level, urine myoglobin, and additional laboratory work-up as indicated, including a number of possible rheumatological/antibody tests (i.e., consider whether a rheumatologist consultation is indicated and could guide need for rheumatoid factor, antinuclear antibody, anti-smooth muscle, antisynthetase [such as anti-Jo-1], and/or signal-recognition particle antibodies). Confirmatory testing may include electromyography, nerve conduction studies, MRI of the muscles, and/or a muscle biopsy. Consider Barium swallow for evaluation of dysphagia or dysphonia.
 

Grade 1	- No dose modifications.	For Grade 1
		
 
Monitor and closely follow up in 2 to 4 days for clinical symptoms and initiate evaluation as clinically indicated.
 

		- Consider Neurology consult.

		
 
Consider, as necessary, discussing with the Clinical Study Lead.
 

Grade 2	
 
Hold study drug/study regimen dose until resolution to Grade ≤1.
 
Permanently discontinue study drug/study regimen if it does not resolve to Grade ≤1 within 30 days or if there are signs of respiratory insufficiency.
 
	For Grade 2  Monitor symptoms daily and consider hospitalization.  Consider Rheumatology or Neurology consult, and initiate evaluation.  Consider, as necessary, discussing with the Clinical Study Lead.  If clinical course is rapidly progressive (particularly if difficulty breathing and/or trouble swallowing), promptly start IV methylprednisolone 2 to 4 mg/kg/day systemic steroids along with receiving input from Neurology consultant  If clinical course is not rapidly progressive, start systemic steroids (e.g., prednisone 1 to 2 mg/kg/day PO or IV equivalent); if no improvement within 2 to 3 days, continue additional work up and start treatment with IV methylprednisolone 2 to 4 mg/kg/day  If after start of IV methylprednisolone at 2 to 4 mg/kg/day there is no improvement within 3 days, consider additional  immunosuppressive therapy such as TNF inhibitors (e.g., infliximab), IVIG or plasmapheresis, or other therapies based on the discretion of the treating specialist consultant or relevant practice guideline Caution: It is important to rule out sepsis and refer to infliximab label for general guidance before using infliximab.

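### Section 25.3.4 gives durvalumab one interrupt-and-wait rule for all Grade 2 or higher toxicity, but Appendix 7, which it cites as its source, requires a permanent stop for several Grade 2 events

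*Protocol*

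**What the plan says.** Section 25.3.4 of the protocol opens by attributing its rule to section 25.3.3 and Appendix 7, and then says that "durvalumab treatment should be interrupted if patients experience any Grade ≥2 toxicity". After an interruption, "trial treatment may be delayed for up to 12 weeks until these toxicities have resolved to Grade ≤1 or returned to baseline". It adds: "Repeat dose interruptions are allowed as required, for a maximum of 12 weeks on each occasion". Its one criterion for permanent discontinuation is being off treatment for more than 12 weeks. It names no event as an exception.

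Appendix 7 (the durvalumab toxicity management guidelines dated 06 August 2024) works event by event:

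- Myocarditis: "If Grade 2-4, permanently discontinue study drug/study regimen".
- Diarrhoea/colitis row: "PERMANENTLY DISCONTINUE STUDY DRUG FOR ANY GRADE OF INTESTINAL PERFORATION".
- General considerations: "Permanently discontinue study drug/study regimen for life-threatening (Grade 4) imAEs, recurrent severe (Grade 3) imAEs", the latter where systemic immunosuppression is needed.
- Grade 2 myositis: "Permanently discontinue study drug/study regimen if it does not resolve to Grade ≤1 within 30 days or if there are signs of respiratory insufficiency". Grade 3 carries the same 30-day limit.
- Isolated type 1 diabetes: "Only hold study drug/study regimen in setting of hyperglycemia when diagnostic workup is positive for diabetic ketoacidosis".

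**The concern.** Section 25.3.4 is the body text on whether durvalumab is held and whether it may restart. Because it claims to report what Appendix 7 directs, a reader has little reason to suspect that Appendix 7 says something different. Read as written, a patient whose Grade 2 myocarditis or Grade 3 pneumonitis settles to Grade 1 within 12 weeks meets no stop criterion in that section, whereas Appendix 7 requires permanent discontinuation in both cases. Section 16.1 lists both among the durvalumab adverse events of special interest.

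The misreport also runs the other way: section 25.3.4 asks for a hold in situations where Appendix 7 lets treatment continue. At stake are patient safety and durvalumab exposure in Part 2.

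**Working it through.** No sample size or error rate is involved, so the check sets section 25.3.4 beside each row of the Appendix 7 table of specific immune-mediated reactions.

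**Counting convention.** Hepatitis is counted once. The separate hepatitis block for patients with liver cancer or liver involvement is left out. For the main hepatitis row, which is banded by multiples of the upper limit of normal (ULN), ALT or AST above 3 and up to 5 × ULN is taken as Grade 2. That gives 16 rows.

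| Appendix 7 action at Grade 2 | Events | Rows |
|---|---|---|
| Permanent stop | Aseptic meningitis (any grade), encephalitis, demyelinating disease (any grade), Guillain-Barré syndrome, myasthenia gravis, myocarditis | 6 |
| Hold, permanent stop if not resolved in 30 days | Myositis/polymyositis | 1 |
| Plain hold until recovery, as in section 25.3.4 | Pneumonitis, diarrhoea/colitis, hepatitis, nephritis, peripheral neuropathy | 5 |
| Hold conditional, discretionary or not needed | Dermatologic (only if lasting more than 1 week), endocrinopathy, raised amylase/lipase, acute pancreatitis | 4 |

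6 + 1 + 5 + 4 = 16. Section 25.3.4 matches 5 of the 16 rows at Grade 2.

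**Grade 3.** The 6 rows above, plus pneumonitis, nephritis and peripheral neuropathy, require a permanent stop: 6 + 3 = 9 of 16. Infusion-related reactions, in a separate table, add another. Hepatitis is not in the 9. It is held at ALT or AST above 5 and up to 10 × ULN but stopped permanently above 10 × ULN, so its row splits.

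**Stops outside the grade-by-row count.** Appendix 7 also stops durvalumab permanently for intestinal perforation of any grade, for confirmed severe cutaneous reactions or Grade 3 pemphigoid, and for recurrent Grade 3 immune-mediated events needing systemic immunosuppression. In the last case section 25.3.4 allows repeat interruptions.

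**Myositis recovery time.** Section 25.3.4: 12 weeks × 7 = 84 days. Appendix 7: 30 days. Difference: 84 − 30 = 54 days, during which Appendix 7 has already stopped the drug and section 25.3.4 has not.

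**Over-holding.** Appendix 7 treats isolated hypothyroidism without interruption, holds for isolated type 1 diabetes only with ketoacidosis, and continues through isolated enzyme rises without pancreatitis. Section 25.3.4 would interrupt all of these at Grade 2 or above.

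**Precedence.** Sections 25.3.2 and 25.3.3 point to Appendix 7, but no body clause says that it prevails where section 25.3.4 differs. The rule in section 25.1 to take the more conservative action applies only between the olaparib and durvalumab guidelines. Section 25.1.2 permits stopping for unacceptable toxicity but does not require it for these events.

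**Section 25.3.3.** It cites the guidelines twice as Appendix 9, although the protocol's appendices end at 7. It also describes them as being for durvalumab monotherapy, although Part 2 gives a combination and the title of the guidelines covers combinations. The distinction matters for Grade 3 colitis: Appendix 7 directs hold and resume for monotherapy, but an investigator decision in discussion with the AstraZeneca study lead for durvalumab combined with products other than tremelimumab.

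**Patients exposed.** Cohorts F and G: 8 + 15 = 23 at most (section 5.1), and fewer on durvalumab, because ineligible patients receive olaparib alone.

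**The case against.** The strongest reply is that the reader is sent to Appendix 7 repeatedly. Section 16.1 says the detailed guidance is there. Appendix 7 itself says that dose modification is to be done in accordance with it, and section 25.3.3 offers trial-team advice in case of doubt. On that reading section 25.3.4 is a general summary, subject to the specific rows of its source. It is also headed as covering interruptions, and its 12 weeks is a ceiling, within which a 30-day limit fits.

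This lowers the practical risk: an investigator who opens Appendix 7 finds the right action. It does not remove the contradiction. Section 25.3.4 goes beyond interruption by setting a recovery period, allowing repeats and stating one stop criterion. A ceiling of 12 weeks followed by a stop after 12 weeks leaves nothing in that section to end treatment at 30 days. The status of Appendix 7 is also not wholly clear, because its general considerations call it a recommendation to support investigators.

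The counts depend on convention. Counting the liver-tumour hepatitis block separately gives 6 of 17. Adding instead the three residual tables (other immune-mediated, infusion-related and non-immune-mediated) gives 6 of 16 + 3 = 19. Five of the six stop rows are neurological. The numerator does not change, and row counts say nothing about how often these events occur. It is also fair that over-holding is the cautious direction and the lesser part of the problem, and that the Appendix 9 references are stale numbers pointing to an identifiable document.

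**Conclusion.** The concern holds. Section 25.3.4 misreports the source it cites. At Grade 2, Appendix 7 requires a permanent stop in 6 of 16 event rows, and it gives myositis 30 days to recover where the body text gives 84. At Grade 3, 9 of 16 rows are permanent stops, on the convention that hepatitis, which splits by severity band, is not counted.

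The reach is limited: at most 23 patients, in Part 2 only. The documents give no rates for these events, so no number of affected patients can be stated. Even so, this is a safety rule that is wrong as written, and it should be corrected.

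**What to change.** Replace the rule in section 25.3.4 with wording to this effect: durvalumab is continued, held or permanently discontinued by event and grade as specified in Appendix 7, which governs; the delay of up to 12 weeks and the repeat interruptions apply only to events for which Appendix 7 permits restart; and any shorter limit in Appendix 7 applies.

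In section 25.3.3, change Appendix 9 to Appendix 7 in both places and delete the words restricting the guidelines to durvalumab monotherapy.

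The cost is one rewritten paragraph and three small wording changes at the next amendment, with no extra visits, tests or patients.
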